## STUDY SUMMARY

Study Title	Recalculating breast cancer risk and exploring the experience of receiving updated breast cancer risk estimates in women with a family history of breast cancer
Short title	Updated breast cancer risk estimates
Study Design	Mixed methods, Quantitative/Qualitative
Study participants	Women who attend the Family History, Risk and Prevention Clinic (FHRPC) who were participants in the FH-Risk study (REC form 10/H1008/24) in 2010-2012
Planned size of sample	
Part 1 (risk estimate recalculation on 954 women. All women (between the ages of 25 and 60) will be invited to receive updated risk feedback):
 
Recalculation of breast cancer risk will be performed on 954 women's data from the FH-Risk study. Women in the FH-Risk study consented to:
 
 
• All necessary genetic tests on a blood DNA sample
 
• The measurement of mammographic density
 
• That all information gathered can be stored by the custodians for possible use in future ethically approved research studies.
 
 
Recalculation will be based on SNPs313, high and moderate risk gene analysis, mammographic density and updated risk prediction models (Tyrrer-Cuzickv8, BOADICEAV [CanRisk]).
 
FH-Risk women still in follow up and those who have been discharged from the FHRPC will be given the opportunity to learn of their recalculated risk via a clinic consultation.
 
Part 2 (interviews with 20 women):
 
Up to 20 cross-sectional interviews across the following groups:
 
 
• women who have received an increased breast cancer risk estimate (by at least one category) since their initial estimate
 
• women who have received a decreased (by at least one category) breast cancer risk estimate since their initial estimate
 
 
Part 3 (think-alouds with 30 women):
 
Up to 30 cross-sectional 'think-aloud' interviews across the following groups:
 
 
• women who have received an increased breast cancer risk estimate (by at least one category) since their initial estimate
 

	
 
• women who have received a breast cancer risk estimate that has not changed category since their initial estimate
 
• women who have received a decreased (by at least one category) breast cancer risk estimate since their initial estimate.
 
 
Part 4 (questionnaire study):
 
Between 300 and 400 questionnaires sent to women who:
 
 
• have had a consultation about their updated breast cancer risk from Part 1 of this study.
 

Study Period	3 years
Research Aims	
 
i) To determine change in NICE categories of risk (average, moderate and high risk) when new risk factors are added to standard breast cancer risk models.
 
ii) To explore how much new risk models (including MD, SNP313 and mutation testing) change risk estimates previously communicated to women as part of the FH-Risk study.
 
iii) To explore whether a change in breast cancer risk affects credibility of how risk is calculated and communicated to women, including trust in its use
 
iv) To use the findings to understand how and in what format(s) changes to breast cancer risk estimates should be communicated in the future to enable women to properly understand change in risk, potential change in management and manage emotional sequelae
 
v) To use the findings to create information materials to communicate changes in breast cancer risk and assess their usability
 
vi) To use the findings to develop a questionnaire to be given to women who previously took part in the FH-Risk study and assess the impact of changed risk in a definitive study
 

Funders & contact details	
NIHR Manchester Biomedical Research Centre Cancer Prevention and Early Detection Theme; [name], University of Manchester, Manchester Cancer Research Centre, [name] Email address: [contact] [contact]
 
This study has been funded by an MRC PhD studentship, awarded to [name] – MR/N013751/1

## 1.0 STUDY PROTOCOL

### 1.1 Research abstract

Estimation of breast cancer risk is important since it enables selection of a high and moderate risk population who benefit from more frequent breast screening and the introduction of targeted measures to reduce risk such as lifestyle change, chemoprevention and risk reducing surgery. Traditionally, risk is estimated by combining information concerning family history and non-familial factors, such as age of menarche and first pregnancy. Subsequent management is related to the degree of risk (high, moderate or average) according to NICE guidelines. Members of the research team and others have added mammographic density (MD) and breast cancer risk associated single nucleotide polymorphisms (SNPs) to risk models which improves the accuracy of risk estimation but which may change the original given risk and risk management given before the updated models became available. The objective of this study is to quantify change in risk and risk management when MD and SNPs are incorporated into two standard models (Tyrer-Cuzick v8 & BOADACEA V). A second objective of the study is to determine the psychological effects of change of risk and management. This study will use participant data from the Family History Risk (FH-Risk) study to recalculate risk. The FH-Risk study population consists of 954 women referred to the Family History Risk and Prevention Clinic (FHRPC) between 2000 and 2012 who gave informed consent for DNA testing and estimation of MD as part of the FH-Risk study which recruited between 2010 and 2012. Change in risk and management will be calculated by comparing given risk at the time of clinic entry compared with re-estimated risk when MD and SNPs are added to the risk models according to NICE guidelines. Risk will be estimated retrospectively at the time of entry to the clinic and the time of latest follow up. All of those who took part in the FH-Risk study will be given the opportunity to discuss their updated risk.

Following the risk update consultation a sample of women will be asked whether they would like to take part in an interview to assess the psychological effects of the change, as well as their views and perceptions of the change. These interviews will inform the development of information materials for communicating recalculated risk. These materials will be appraised via 'think aloud' interviews with women from the FH-Risk study who have received their recalculated risk. The results of this study are likely to inform the next iteration of NICE management guidelines for Family History Clinics, as well as inform the creation of patient facing information materials to aid patient - healthcare professional communication. The findings will also be used to develop a questionnaire to be given to women who

previously took part in the FH-Risk study (and who have been discharged from the clinic) to assess the psychological impact of changed risk in a definitive study.

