## 2.0 AIMS & OBJECTIVES OF THE STUDY

### 2.1 Aims

The aims of this study are:

- i) To determine change in NICE categories of risk (average, moderate and high risk) when new risk factors are added to standard breast cancer risk models.
- ii) To explore how much new risk models (including MD, SNP313 and mutation testing) change risk estimates previously communicated to women as part of their management plan at first attendance at the FHRPC.
- iii) To explore the experiences of risk estimate changing over time in women with a family history of breast cancer. This will be assessed by using the re-evaluated risk estimates using the TC v8 and BOADICEA (with added MD, SNP313 and mutation testing) in a sub-sample of FH-Risk study participants and conducting qualitative interviews with women who choose to receive their re-evaluated breast cancer risk estimate.
- iv) To determine whether change in management differs between the three density measures in the Tyrer-Cuzick model. (BIRADS, Predictive VAS AND Volpara).
- v) To compare the degree of management change between the Tyrer-Cuzick (v8) and the BOADICEA model (v5) (Can-Risk).
- vi) To create information materials informed by participant interviews to communicate and inform women of their breast cancer risk re-evaluation and have these materials appraised by a sample of the FH-Risk women who have received their recalculated risk.

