4. *I consent to the transfer of coded data with no personal identifiers for the purpose of the current research study looking at common genetic changes associated with breast cancer risk to any sponsor of the research*
5. *I agree that the information gathered can be stored by the custodians, University Hospital of South Manchester Foundation Trust, for possible use in future ethically approved research studies as described in the information sheet.*
6. *Would you like to receive your updated breast cancer risk information? (Please tick one box below)*

Archived information that women consented to for the use in other ethically approved studies include: demographic details, family pedigree including any history of cancer (current age or age of death of any relative, type of cancer and age at diagnosis), reproductive history (age at menarche, age at first pregnancy, duration of episodes of lactation and age at menopause if applicable), history of benign breast disease (including number of benign biopsies), artificial oestrogen exposure (duration of oral contraceptive pill usage, hormone replacement or fertility drugs) and morphometric information (BMI is also assessable from self-reported height and weight estimates from the women). In addition, the database stores an absolute lifetime risk calculated using the modified Claus or Tyrer-Cuzick models. The database also contains information regarding breast cancer incidence until at least January 2015. This will be extended during the study to December 2020. Although MD was not included in the risk estimates provided as part of FH-Risk, women did consent to their MD being accessed, calculated and fed back to them and this data will be accessed under their original consent (See appendix 1).

Members of the research team who are consultants and who were also part of the FH-Risk research team have permission (as they are part of the clinical care team) to access the above data (including DNA data) which participants consented to in order to perform the recalculation of risk.

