### **Risk estimation models to be used to recalculate risk**

#### ***Calculation using Tyrer-Cuzick Version 8***

Phenotypic risk will be assessed using predicted remaining 10-year and lifetime risks to age 85 from the TC model V8 (Tyrer 2004; <http://www.ems-trials.org/riskevaluator/>). The following information from the original risk questionnaire collected before 2012 will be incorporated: age at baseline; first and second-degree relatives (age affected by breast and ovarian cancer or current age or age at death); age at first child, menarche and menopause; height and weight; and history of prior benign breast disease. Changes in these risk parameters will be assessed at subsequent clinical appointments and incorporated into the model.

Version 8 of the TC Model differs from V6 in that risk is estimated until the age of 85 (from 73 or 80 years) and because breast cancer risks have generally increased since V6 was developed (Tyrer et al., 2004). Thus, women will have in any case somewhat higher risks than previously given at their initial

appointment. However they still may end up with a lower risk estimate than originally given when MD and SNPs are taken into account (Brentnall et al., 2015).

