#### **1. Objectives**

Primary

- vii) To determine change in NICE categories of risk (average, moderate and high risk) when new risk factors are added to standard breast cancer risk models.

- viii) To explore how much new risk models (including MD, SNP313 and mutation testing) change risk estimates previously communicated to women in the FH-Risk study, between their first referral and their latest visit to the FHRPC
- ix) To compare 10-year and lifetime risk estimates given by Tyrer-Cuzick (v8) and the BOADICEA model (v5) (Can-Risk)

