### **3.7 Part 4: Communicating an updated breast cancer risk: A questionnaire study**

#### **Questionnaire rationale and objectives**

It is well documented in the literature that women either under or over-estimate their risk of developing breast cancer even after the provision of a clinically-derived risk estimate. It is unknown however what women understand about their risk and how they describe their risk following an update which incorporates new strong independent risk factors.

In this questionnaire study we want to examine the relationship between objective risk (i.e. the updated clinical estimate) and women's subjective understanding of their risk following the provision of an updated clinically-derived breast cancer risk estimate. With this we also want to examine women's breast cancer risk knowledge, including whether they perceived a change to their risk and cancer worry.

Specific objectives include:

- To examine whether there is a difference between objective and subjective risk, looking at first risk given in the first FH-Risk study, updated risk (provided in Part 1 of this study) and women's perceived risk.
- To examine the predictors of subjective risk, including objective risk factors such as family history, PRS, breast density and weight.
- To examine whether women have perceived a change to their risk.
- To examine women's breast cancer risk knowledge, including factors which have contributed to their risk.

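### Change from given to re-estimated risk mixes a model-version effect with the effect of density and SNPs, and the plan does not separate the two

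*Combined protocol and SAP*

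**What the plan says.** Section 1.1 gives the objective as quantifying change in risk and management when MD and SNPs enter two standard models. The scoring rule follows: "Change in risk and management will be calculated by comparing given risk at the time of clinic entry compared with re-estimated risk". The same section adds: "Risk will be estimated retrospectively at the time of entry to the clinic and the time of latest follow up".

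The communicated figure is also the reference elsewhere. The second aim in section 2.1 asks how far new models "change risk estimates previously communicated to women as part of their management plan at first attendance at the FHRPC". The second primary objective of the Statistical Analysis Plan (SAP, within section 3.1) asks how far they "change risk estimates previously communicated to women in the FH-Risk study". The first Part 4 objective (section 3.7) examines risk "looking at first risk given in the first FH-Risk study, updated risk (provided in Part 1 of this study) and women's perceived risk".

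On where the given figure came from, section 3.1 says "the database stores an absolute lifetime risk calculated using the modified Claus or Tyrer-Cuzick models".

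On TCv8, section 3.1 says that it differs from V6 because "risk is estimated until the age of 85 (from 73 or 80 years) and because breast cancer risks have generally increased since V6 was developed". It draws the consequence itself: "Thus, women will have in any case somewhat higher risks than previously given at their initial" appointment. It adds that MD and SNPs may still bring the final figure below the original one.

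The SAP takes lifetime risk to age 80 for both new models, whereas the TCv8 methods say 85. The SAP's primary endpoints include runs with classical factors alone, with MD added, and with MD and SNPs added. SAP analysis (iii) uses those runs to compare TCv8 with BOADICEA. Analysis (i) cross-tabulates NICE categories at entry against last follow-up.

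**The concern.** The objective concerns the effect of two new risk factors, while the scoring rule compares two figures that can also differ in model, end age and baseline incidence. By the protocol's own account, a woman given a V6 figure whose MD and SNP results are neutral would get a higher lifetime risk at the same age. That rise carries no information about density or SNPs, but the rule would count it with theirs.

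The fixed 17% and 30% lifetime cut-points apply to both figures, so some category changes could come from the change of model alone. Sections 1.2 and 1.3 ask whether NICE guidelines should change to include the new models, and section 1.1 expects the results to inform the next guideline. A change credited to the wrong source would weaken that use. Movement by at least one category also defines the Part 2 and Part 3 sampling groups.

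**Working it through.** **1. The plan's own figures.** The plan gives no size for this effect. The nearest figures are from the pilot (section 1.2): 53, 40 and 13 of 106 women moved down, stayed or moved up, and these reproduce as 50%, 38% and 12%. The pilot compared TC with MD and SNPs against TC alone. It is a like-for-like contrast and says nothing about the version effect.

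**2. What each comparison contains.** Write the total change from given to updated risk as (a) given figure to TCv8 classical factors at entry age, plus (b) TCv8 classical factors to TCv8 with MD and SNPs at the same age and end age, plus (c) ageing and changed inputs up to latest follow-up.

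- Section 1.1 rule, at entry age: (a) + (b).
- Section 1.1 rule, at latest follow-up: (a) + (b) + (c).
- SAP analysis (i), if entry means the given figure: (a) + (b) + (c).
- SAP analysis (i), if entry is recalculated with the same inputs: (c) only. The communicated estimate then never enters, and the second primary objective has no analysis.
- SAP nested runs: these yield (b), but are assigned to the TCv8-BOADICEA comparison.

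No planned analysis reports (a) and (b) separately.

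**3. Illustration of the horizon part of (a), V6 figures only.** R85 = 1 − (1 − R) × exp(−h × years added). *Assumptions, not in the documents:* annual hazard h of 0.2% to 0.8% in the added years, no competing mortality, neutral MD and SNPs, same age, given risk R of 10% to 35%.

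| Given figure ran to | Years added | Added points | Lowest R that reaches 17% | Lowest R that reaches 30% |
|---|---|---|---|---|
| 80 | 5 | 0.6 to 3.5 | 13.6% to 16.2% | 27.1% to 29.3% |
| 73 | 12 | 1.5 to 8.2 | 8.6% to 15.0% | 22.9% to 28.3% |

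Example: 20% to age 80 becomes 1 − 0.80 × exp(−0.01) = 20.8% at the low hazard and 1 − 0.80 × exp(−0.04) = 23.1% at the high one. She stays moderate. The higher incidence in TCv8 would come on top; the documents do not quantify it.

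**4. At latest follow-up.** Remaining risk = 1 − (1 − R85)/(1 − e), with e the risk already passed (assumed 2% to 5%). For given risks of 20% to 32%, the net change runs from −3.4 points (20%, h = 0.2%, 5 years added, e = 5%) to +5.8 points (20%, h = 0.8%, 12 years added, e = 2%). The sign is not fixed.

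**5. Modified Claus figures.** Ages 73 and 80 are stated for V6 only. Section 1.2 gives expected-to-observed ratios of 1.22 for modified Claus and 0.81 for Tyrer-Cuzick. If both applied to the same women, the switch alone would multiply predicted risk by 0.81/1.22 = 0.66, a fall. This is only an indication that the direction is open: the 0.81 is for an earlier Tyrer-Cuzick version, and Table 2 as printed sets an interval of 0.85 to 1.41 beside it.

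**6. After the split.** With one version, one age and one end age on both sides, neutral MD and SNPs give a change of zero in (b) by construction.

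**The case against.** The strongest reply is that the second aim asks how far new *models* change the communicated figure, and that end age and incidence belong to the new model. On that view total change is a proper estimand. This stands, and it is why the total should be kept. It does not cover the first aim, which concerns adding new factors to standard models, or the objective in section 1.1.

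A second reply is that the SAP, not the abstract, governs. Analysis (ii) takes change in continuous risk from TCv8 and BOADICEA, and lifetime risk runs to age 80, so both sides might share model and horizon. That reading is possible, but analysis (i) does not say which entry figure it uses, and the age of 80 conflicts with 85 in the methods. Adopting 80 would close the gap for V6 figures given to 80. It would leave seven years for those given to 73, and the incidence part.

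A third reply is that the nested runs already isolate MD and SNPs. The outputs are indeed planned, but their use for this purpose is not. The 10-year endpoint has no end-age mismatch, but the archived given figure is described as a lifetime risk and the NICE cut-points in Table 1 are lifetime.

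A reader might infer that every woman with neutral MD and SNPs is scored as increased. The documents do not support that: the stated shift is V6 to V8 only, the Claus direction is open, category changes arise only near a cut-point, and remaining risk at follow-up can reverse the sign.

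**Conclusion.** The concern holds in a limited form. The given-versus-updated change mixes a model-version effect with the MD/SNP effect, and no planned analysis separates them. For V6 figures at an unchanged age, the protocol itself says the version effect is upward. For modified Claus figures neither its direction nor the end age is documented.

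Its size in this cohort cannot be computed from the documents. The 0.6 to 8.2 points and the crossing zones near 17% and 30% rest on the assumed hazards and cover the horizon alone.

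A reader might go on to multiply the crossing zones by the 50.3% moderate-risk share in section 1.2, to get a percentage of women wrongly moved up. That is not supported. The share describes the whole clinic since 1987 rather than these 954 women, the mix of Claus, V6-to-73 and V6-to-80 figures is not given, and the late-age hazards are assumed. Nor does the pilot's 12% measure this effect, because its comparator was TC alone.

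**What to change.** Keep the total given-to-updated change for the second aim. In SAP analyses (i) and (ii), split it at entry age into:

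- **(a)** given risk to TCv8 with classical factors alone, as the model-version effect, reported separately for modified Claus and V6 figures;
- **(b)** TCv8 classical factors to TCv8 with MD and SNPs, at the same age and end age, as the effect of the new factors.

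Attribute only (b) to MD and SNPs, and use (b) for the first aim. If the total is taken at latest follow-up, show the remainder due to ageing and changed inputs as its own line. Women with a pathogenic variant receive the CanRisk figure, so their total does not divide along TCv8 lines; list them separately.

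State whether entry in the cross-tabulation is the given or the recalculated figure. The SAP also allows age 40 as the entry point, but (a) needs the age at which the given figure was produced. Reconcile the lifetime end age (80 in the SAP, 85 in the TCv8 methods).

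Where the end age behind a given figure can be recovered, a common-end-age comparison can be a sensitivity analysis. It should not be the main analysis: no section says that the end age was archived, and it answers a different question from the second aim. Leave the Part 4 comparison on the figures that women were actually given.

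Cost: a few sentences in the SAP and one extra table, using classical-only and MD/SNP runs that are already primary endpoints.

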## 1.2 Research background

### Management of breast cancer risk: Family History Clinics

In the 1980's publicity concerning the rise in the incidence of breast cancer and the introduction of breast screening programmes increasingly led women with a family history of the disease, to seek advice concerning management of their personal risk of breast cancer. In response to primary care physicians and colleagues within our breast oncology service, we set up a referral Family History Risk & Prevention Clinic (FHRPC) Manchester, UK in 1987 with a cancer genetics component initiated in 1990. The clinic serves the catchment population of a National Health Service Breast Screening Centre (the Nightingale Centre) which covers a total population of 1.8m, (just over half the population of Greater Manchester) although women at high risk may be specially referred from a population of approximately 5 million in the Northwest Region of England.

During clinic appointments risk was explained, annual breast screening initiated and advice given concerning diet and lifestyle factors which might affect risk. Later genetic testing (1994), chemoprevention (1992) as part of the IBIS I clinical trial) and risk reducing surgery (1994) were introduced. Local (Evans 1994) and, later, national guidelines for management of women with a family history were published for the UK (Eccles 2000, NICE McIntosh 2004), the USA (Hoskins 1995, NCCN Merajver 2003). In the UK NICE guidelines indicate management should be stratified in the clinic. Women estimated to be at high risk ( $\geq 30\%$  lifetime risk) are offered annual mammographic screening until 60, and chemoprevention or risk reducing surgery. Women at moderate risk (17-20% lifetime risk) are offered mammographic screening until 50 and are 'considered' (rather than 'offered' chemoprevention (Table 1)) but not considered for risk reducing surgery. Thus precise estimation of risk is important for management. Since the inception of the FHRPC in 1987, 49.7% of women were at high risk (n=5390) whereas 50.3% were at moderate risk (Howell 2020).

